patient had an emergency department visit on POD 20, due to an unrelated mechanical fall. Importantly, there were no major complications in either group requiring procedural interventions, new prescriptions, or additional interventions. Recently, a study by Kisby et al was published examining SDD after robotic-assisted sacrocolpopexy. In this retrospective study, 80 women underwent SDD compared to 192 who were discharged on  $\geq$ POD 1. This study found no difference in unplanned provider visits, emergency department visits or readmissions between the groups.

**We hypothesize that an ERAS protocol utilizing SDD for minimally invasive sacrocolpopexy is as safe as those that utilize discharge on POD 1 while incurring less total procedure-related costs and being acceptable as a post-op management plan for patients.** The *objective of this study* is to provide data which are necessary to widely implement SDD after a minimally invasive sacrocolpopexy. The results of this research *will have a significant impact* on increasing patient satisfaction, minimizing resource utilization, and improving clinical practice patterns in the field of urogynecology, both for this procedure and potentially other surgeries within our subspecialty.

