### **Specific Aims**

**Aim 1.** To compare the incidence of adverse events in patients following a SDD protocol for minimally invasive sacrocolpopexy compared to those patients discharged on POD 1.

We hypothesize that there is no difference in the incidence of adverse events between SDD compared to discharge on POD 1 after minimally invasive sacrocolpopexy. Using the *Epic* electronic medical record (**EMR**), we will evaluate 1) the number of unscheduled office visits, patient-initiated calls for a surgery-related complication, emergency department visits, and readmissions/reoperations of patients who had a SDD protocol and 2) the severity of any adverse events using the Clavien Dindo Scale. We will utilize patient phone calls to inquire about any of the aforementioned events outside of our institution. We will compare incidence of postoperative adverse events between patients undergoing SDD versus a historical control group who were discharged on POD 1.

**Aim 2.** To compare the total procedure-related costs associated with SDD compared to discharge on POD 1 for minimally invasive sacrocolpopexy.

We hypothesize that the total costs associated with SDD following minimally invasive sacrocolpopexy is less than the same procedure with discharge on POD 1. We will utilize data from the billing function of *Epic* EMR to compare total procedure-related costs for each approach to minimally invasive sacrocolpopexy.

**Aim 3.** To determine patient satisfaction with SDD after minimally invasive sacrocolpopexy.

We hypothesize that patients will be satisfied with SDD after minimally invasive sacrocolpopexy. We plan to address this aim using a series of validated measures.

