### **3. Data Collection**

The EMR will be reviewed to collect preoperative, intraoperative, and POD 0 data points. We will use the following method to identify the occurrence of a procedure-related adverse event: The EMR will be reviewed for patient phone calls for a procedure-related complication, unscheduled office visits, emergency department visits, hospital readmissions or reoperations within 30 days, and adverse events occurring up to 6 weeks post-operatively. The adverse events of interest will include the following:

- Wound infection
- Hematoma
- Transfusion
- Pelvic abscess
- Osteomyelitis
- Venous thromboembolism (deep vein thrombosis or pulmonary embolism)
- Delayed bowel or urinary tract injury
- Bowel obstruction or ileus
- Cardiac or pulmonary complication
- Neurologic injury

We will also employ an approach that will allow us to capture events that may have been handled outside of the CCHS or in institutions that do not utilize *Epic*. To capture these data points if they exist, we will contact participants by telephone on POD 1 (within 24 hours of surgical completion time) to determine if they received any care from a facility outside of the CCHS and then again at the post-operative follow up visit, which generally occurs at 6 weeks. We will then use these data with the Clavien Dindo Scale to determine the severity of the adverse event, with a grade 3 or higher considered to be a serious adverse event, and we will compare this proportion to the reference proportion of 26.3%. A proportion of patients with grade 3 or higher less than 45.1% will be considered non-inferior to the reference.

As part of the effort to characterize the patient population, we will extract data regarding total procedure-related costs using the EMR. We will assess satisfaction using the quality of recovery questionnaire, visual analog scores for postoperative pain, and a patient satisfaction survey described by Fountain et al at the postoperative visit, which uses a Press Ganey scale for responses (See Appendix A). Please see data collection sheet for a comprehensive list of planned data points.

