### **4. Statistical Plan**

*Statistical analysis:* Categorical variables will be presented as n/N (%) with 95% confidence intervals. Continuous variables will be presented as mean +/-SD or median [range]. A Pearson's chi-square test or Fisher exact test will be used for frequencies and proportions of categorical values and t test or the non-parametric Wilcoxon rank sum test for mean values of continuously measured variables. P values  $\leq 0.05$  will be considered statistically significant and we will use SAS (version 9.4, The SAS Institute, Cary NC) as our statistical package to perform these analyses. The primary investigator will perform the statistical analysis with assistance from the WHI statistician.

We will use data from a historical control group discharged on POD 1 after minimally invasive sacrocolpopexy to examine Aim 1 and Aim 2. This is a cohort of 60 women matching our eligibility criteria from a prospective randomized trial of two different types of lightweight polypropylene mesh (IRB #14-354). This study completed recruitment 2017. It consists of a group of women who underwent minimally invasive sacrocolpopexy using the same surgical approaches, at the same institutions (main campus, Fairview and Hillcrest), and performed by the same surgeons as our study. The primary difference is that participants in that study and the cohort proposed here is that all participants were discharged home on POD 1. We will utilize this cohort to compare the incidence and severity of procedure-related adverse events and costs between SDD and POD 1. Comparisons on outcome measures will be done using either an ANOVA analysis or a student's t test for parametric continuous outcomes, a Kruskal-Wallis or Mann Whitney U test for non-parametric outcomes and a Chi-square test for all categorical outcomes. Logistic regression will be performed to control for confounding variables.

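### Aim 1 hypothesises equal safety against the 60 POD 1 controls, but the between-cohort plan is difference testing with no margin and no stated interval for the difference, so P>0.05 cannot support it

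*Combined protocol and SAP*

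**What the plan says.** Background & Significance states the overall hypothesis: "We hypothesize that an ERAS protocol utilizing SDD for minimally invasive sacrocolpopexy is as safe as those that utilize discharge on POD 1". Aim 1 in Specific Aims repeats it as a null: "We hypothesize that there is no difference in the incidence of adverse events between SDD compared to discharge on POD 1". The same aim names the comparator: "We will compare incidence of postoperative adverse events between patients undergoing SDD versus a historical control group who were discharged on POD 1".

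Section 4 (Statistical analysis) confirms the assignment: "We will use data from a historical control group discharged on POD 1 after minimally invasive sacrocolpopexy to examine Aim 1 and Aim 2". That cohort has 60 women. For the comparison, the section lists "a Kruskal-Wallis or Mann Whitney U test for non-parametric outcomes and a Chi-square test for all categorical outcomes". Its general paragraph also allows Fisher: a "chi-square test or Fisher exact test will be used for frequencies and proportions of categorical values", with significance at P≤0.05. A logistic regression is planned to deal with confounding; its covariates, its interval and its role in the conclusion are not given. Intervals appear once: "Categorical variables will be presented as n/N (%) with 95% confidence intervals".

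The only non-inferiority rule is in section 3: "A proportion of patients with grade 3 or higher less than 45.1% will be considered non-inferior to the reference". The reference there is a fixed 26.3%, and the sample size of 45 (47 with dropout) is derived from that one-sample test.

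**The concern.** A test of difference can reject equality; it cannot establish it. Aim 1 and the overall hypothesis are claims of similarity to POD 1 discharge, and the 60 controls are the comparison group assigned to them. No margin is set for that comparison, no interval is specified for the SDD-minus-control difference, and nothing says how P>0.05 will be read. With 45 and 60 patients, a non-significant result is compatible with equal safety and also with a large excess of serious events. The protocol's stated purpose is to supply the data needed for wide adoption of SDD, so a non-significant P value reported as equal safety would be an unsupported safety claim with practical consequences.

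**Working it through.** **Inputs.**
- From the documents: 45 evaluable SDD patients (section 4, Sample size); 60 controls and P≤0.05 (section 4, Statistical analysis); event rates of 5.4%, 12% and 26.3% (section 4, Sample size).
- Assumptions: two-sided testing, since sidedness is not stated for these comparisons; 5.4% and 12% used as grade 3 or higher rates, although the plan ties only 26.3% to grade 3; a doubling of risk as the benchmark, which is mine. The 20% row below is an intermediate value for illustration.

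**Step 1. The plan's own figure.** One-sample exact binomial, n = 45, reference 26.3%, one-sided alpha 0.05 (assumed; not stated there). The critical count is 18, because P(X≥18 | 0.263) = 0.031 and P(X≥17 | 0.263) = 0.061. Power at 45.1% is P(X≥18 | 0.451) = 0.798. The stated 80% power at 45.1% therefore reproduces, but it belongs to the test against a fixed value. For 26.3% versus 45.1% with 45 and 60 patients, two-sided 0.05, power is 53% (Pearson) or 47% (Fisher).

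**Step 2. Chance of missing a true doubling, 45 versus 60.** Power is the sum of Bin(i; 45, p1) × Bin(j; 60, p2) over all tables (i, j) with p≤0.05, where p1 = 2 × p2.

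| Control → SDD rate | Power, Pearson | Power, Fisher | Missed |
|---|---|---|---|
| 5.4% → 10.8% | 0.179 | 0.129 | 82–87% |
| 12% → 24% | 0.407 | 0.310 | 59–69% |
| 20% → 40% | 0.634 | 0.554 | 37–45% |
| 26.3% → 52.6% | 0.796 | 0.760 | 20–24% |

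Power for a doubling passes one half at a control rate of about 15% (Pearson) or 18% (Fisher).

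**Step 3. Two results that P≤0.05 treats alike.** The Newcombe interval for d = p1 − p2 uses each group's Wilson limits (l, u): lower = d − √[(p1 − l1)² + (u2 − p2)²], upper = d + √[(u1 − p1)² + (p2 − l2)²].
- 11/45 (24.4%; Wilson 14.2–38.7%) versus 7/60 (11.7%; Wilson 5.8–22.2%): d = +12.8 points, Pearson p = 0.086, Fisher p = 0.117, interval −1.9 to +28.2 points.
- 5/45 (11.1%; Wilson 4.8–23.5%) versus 7/60: d = −0.6 points, Pearson p = 0.93, Fisher p = 1.00, interval −12.8 to +13.2 points.

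Both are non-significant. In the first the observed rate is about double. In the second the rates nearly agree, yet an excess larger than 12 points is not excluded.

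**Step 4. Precision available.** With equal rates, SE = √[p(1 − p)(1/45 + 1/60)] = 0.0446, 0.0641 and 0.0868 at 5.4%, 12% and 26.3%. Multiplying by 1.96 gives half-widths of 8.7, 12.6 and 17.0 points.

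**Step 5. Smallest margin this sample could meet.** With both rates at 12%, one-sided 2.5% and 80% power: (1.960 + 0.842) × 0.0641 = 0.180, or about 18 points.

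**The case against.** Four points can be made for the plan.

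*The primary decision has its own non-inferiority rule.* True. The 45.1% rule for serious adverse events stands apart from this comparison. A reader might infer that the primary conclusion fails on this point; the documents do not support that. The rule does not answer the point either, because it never uses the POD 1 controls to which section 4 assigns Aim 1.

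*The comparison is not limited to a chi-square test, and precision is not wholly hidden.* Also true. Logistic regression is planned and could yield an odds-ratio interval, and the per-group 95% intervals would show that both rates are imprecise; Newcombe's interval is built from just such per-group limits when the Wilson method is used. So it would be too strong to say that a difference test is the only analysis or that the plan gives no information on precision. What is missing is narrower: a stated estimate and interval for the difference, a value to judge it against, and any role for the regression in the conclusion.

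*No passage says that P>0.05 will be read as equal safety.* Correct, and that intention should not be attributed to the investigators. But the stated hypothesis is no difference, the stated tool is a difference test, and no other reading is offered.

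*The size depends on assumed rates.* This stands. At 26.3%, the one rate the plan ties to grade 3, the test would usually detect a doubling (power 76–80%). The larger miss rates rest on 5.4% and 12%, although the plan itself considers 12% the more representative adverse event incidence. The documents give no cohort rates for calls, unscheduled visits, emergency visits or readmissions, so nothing is computed for those.

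**Conclusion.** The concern holds as a gap in the analysis and reporting of Aim 1's historical comparison; the primary decision rule is untouched. A non-significant result from 45 versus 60 patients cannot support the equal-safety hypothesis. If the grade 3 or higher control rate is 12%, a doubling is missed 59–69% of the time, and equal rates still carry an uncertainty of about ±12.6 points. At 26.3% a doubling is missed 20–24% of the time, but the half-width grows to 17.0 points. These figures assume two-sided testing, full cohorts of 45 and 60, and doubling as the benchmark. The central point needs none of them: without a margin, or an interval for the difference, a difference test does not address a hypothesis of similarity. The change is worth making because it is cheap.

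**What to change.** In section 4 (Statistical analysis), for grade 3 or higher events and the other binary Aim 1 outcomes:

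1. Base the between-cohort conclusion on the SDD-minus-control risk difference with a Newcombe or Miettinen-Nurminen 95% interval.
2. Report beside it the confounder-adjusted estimate and 95% interval from the planned logistic regression, as far as event counts allow. The crude interval should not stand alone in a non-randomised historical comparison. At 12% in both cohorts, about 0.12 × 105 = 12.6 events are expected, so few covariates can be carried.
3. State that a non-significant chi-square or Fisher test will not be taken as evidence of equal safety.
4. Label the historical comparison descriptive (estimation only) unless a justified margin is fixed before the data are compared. Because the control trial finished recruiting in 2017, any margin should be justified independently of the control results.
5. Align the hypothesis wording in Background & Significance and in Aim 1 with whichever option is chosen.

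The cost is wording. The crude interval needs the same counts as the planned chi-square test, the regression is already planned, and no patients are added. The downside is that the sponsor must report wide precision (about ±12.6 points at 12%) and give up any claim of equal safety from P>0.05. Choosing a margin instead would mean about 18 points at 12% for 80% power, which is wide against that base rate; the descriptive label avoids this.

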### **Research Plan**

#### **1. Study Design**

This is a prospective cohort study evaluating safety, cost and patient satisfaction with SDD for patients undergoing minimally invasive sacrocolpopexy for pelvic organ prolapse. A prospectively collected, historical control group who underwent the same surgical procedure will be utilized to compare these outcomes when applicable. SDD will be facilitated in part by a utilizing novel patient education video created for this study and implementing an ERAS pathway. All patients meeting eligibility criteria will be approached for study participation. Outcomes will be assessed on POD 0/1 and at the routine post-operative follow up visit, generally at 6 weeks after surgery.

**Primary outcomes:** The primary outcome of this study is serious adverse events.

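### The plan names no ordinal test for Clavien Dindo severity: its natural reading sends an ordered grade to an unordered chi-square in the supportive between-group comparison

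*Combined protocol and SAP*

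**What the plan says.** Aim 1 (Specific Aims) has two parts: counts of events and contacts, and "the severity of any adverse events using the Clavien Dindo Scale". Section 4 (Statistical Plan) then says of the historical cohort: "We will utilize this cohort to compare the incidence and severity of procedure-related adverse events and costs between SDD and POD 1".

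Tests are assigned by type of variable. For the comparisons on outcome measures, the plan lists ANOVA or a t test for parametric continuous outcomes, then "a Kruskal-Wallis or Mann Whitney U test for non-parametric outcomes", then "a Chi-square test for all categorical outcomes". The opening paragraph of the same section is narrower. It pairs the rank-sum test with continuously measured variables, and Pearson chi-square or Fisher with categorical ones. No sentence says which test applies to Clavien Dindo grade.

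The primary use of the scale is binary. Section 1 states: "The primary outcome of this study is serious adverse events". Section 3 (Data Collection) defines it, "with a grade 3 or higher considered to be a serious adverse event", and says "we will compare this proportion to the reference proportion of 26.3"%, with a result below 45.1% counted as non-inferior.

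**The concern.** Clavien Dindo grades are categories with an order. Read literally, the word all in the chi-square clause leaves no exception for ordered scales, and the opening paragraph reserves the rank test for continuous measurements. On that reading severity goes to a Pearson chi-square.

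That statistic is unchanged if the grade columns are shuffled. It therefore cannot use the information that SDD events lie further up the scale. With six categories (no event, then grades I to V) it also spreads 5 degrees of freedom over a sparse table. If SDD moved women generally towards worse grades, this test would be less likely to show it than a test that uses the order.

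If the sentence is instead taken as ambiguous, the choice between chi-square and Mann-Whitney could be made after the data are seen.

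**Working it through.** **1. The plan's own figure.** One-sided exact binomial, n = 45, reference 0.263, alpha 0.05 (inferred; the sizing paragraph gives no alpha, and one-sided 0.025 does not reproduce 45.1%). The smallest count with tail probability at most 0.05 is 18: P(X >= 18 | 0.263) = 0.031 and P(X >= 18 | 0.451) = 0.798. So 80% power at 45.1% reproduces. It rests on a binary one-sample test, and the choice of test for the full grade does not enter it.

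**2. On a binary outcome no order is lost.** For a 2 x 2 table the Pearson chi-square and the trend statistic differ only by (N - 1)/N. In a worked table with N = 105: 1.553 x 104/105 = 1.538.

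**3. Inputs for the full-grade comparison.**
- From the documents: 45 evaluable SDD women, 60 controls, significance level 0.05 (taken as two-sided).
- Assumed, because the documents give no grade distribution: control grades 0/I/II/III/IV/V = 65/13/10/9/2.5/0.5%, worst grade per woman. Grade 3 or higher is then 9 + 2.5 + 0.5 = 12%, the rate the sample-size paragraph thinks more representative.

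**4. Sparseness.** With no difference, expected counts are n x p. For SDD they are 29.3, 5.9, 4.5, 4.1, 1.1 and 0.2; for controls 39, 7.8, 6, 5.4, 1.5 and 0.3. Six of the 12 cells are below 5.

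**5. Alternative.** A proportional-odds shift: odds of grade k or worse under SDD = OR x the control odds, for every k. At OR 2:
- any event: 0.35/0.65 = 0.538; x 2 = 1.077; probability 1.077/2.077 = 51.9%
- grade 3 or higher: 0.12/0.88 = 0.136; x 2 = 0.273; probability 0.273/1.273 = 21.4%

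**6. Tests.** Pearson X² = sum of (O - E)²/E on (2 - 1)(6 - 1) = 5 df, empty grades dropped, against the Wilcoxon rank-sum test with tie-corrected variance. Power by simulation, mostly 6,000 replicates per setting:

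| Setting | Chi-square | Wilcoxon |
|---|---|---|
| No difference | 3-4% | about 5% |
| Six grades, OR 2 | 25% | 44% |
| Six grades, OR 2.5 | 43% | 66% |
| Six grades, OR 3 | 62% | 83% |
| None / I-II / III or higher, OR 2 | 34% | 41% |
| None / I-II / III or higher, OR 2.5 | 57% | 67% |

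Repeat runs agree to within about 2 points. The three-category gain averages about 8-9 points.

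**7. Other assumed control distributions.** Control grade 3 or higher was set to each rate in the sample-size paragraph. Six grades, chi-square v Wilcoxon:

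| Control grade 3 or higher | OR 2.0 | OR 2.3 |
|---|---|---|
| 26.3% | 27% v 48% | 38% v 64% |
| 12% | 26% v 46% | 38% v 62% |
| 12%, few minor events | 17% v 32% | 26% v 46% |
| 5.4% | 23% v 39% | 33% v 53% |

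OR 2.3 is the plan's own contrast: (0.451/0.549)/(0.263/0.737) = 2.30.

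**8. Other kinds of shift.**
- Incidence rises with the same severity mix: 33% v 50%.
- Extra grade 3 or higher events among otherwise event-free women: 25% v 37%.
- Only grade 3 or higher rises, 26.3% to 45.1%: 29% v 41%. The binary chi-square does better, at 52%.
- Incidence fixed at 35% and only the events worsen (grade 3 or higher 12% to 25%): 34% v 7%. The order of the two tests reverses. With incidence fixed at 40% it is 30% v 9%; restricting that case to women with an event gives 36% v 55%.

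**The case against.** The strongest reply is that the plan never says severity will be tested by chi-square. The same sentence offers Mann-Whitney U, the very test recommended here. This stands in part: routing grade to chi-square is an inference, though the natural one given the opening paragraph of section 4. The gap is that the test is not named.

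A reader might infer that Aim 1 as a whole loses power to detect harm. The documents do not support that. The primary outcome is binary, its comparison is one-sample against 26.3%, and the only stated power belongs to that test (steps 1 and 2). A reader might also infer that a non-significant severity table would serve as the safety conclusion. The written rule for that conclusion is the 45.1% threshold in section 3. Aim 1 does hypothesise no difference, so a null severity result could be cited in support, but the plan makes no decision depend on it.

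Third, ignoring order does not always cost power. If SDD left incidence unchanged and only made events worse, ranking all women would nearly miss it. This stands, and it shapes the fix.

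Fourth, sparse cells are partly covered because section 4 allows Fisher's exact test. That protects the false-positive rate, but an exact test on the unordered table ignores the order too.

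**Conclusion.** The concern holds in limited form. The plan compares an ordered severity grade between groups, assigns it no ordinal test, and by its general rule points to an unordered one. For a general shift to worse grades at odds ratios of 2 to 2.5, that costs about 20 points of power on six grades (44 - 25 = 19; 66 - 43 = 23). The cost is about 8-9 points on three categories and nothing on the binary outcome.

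These figures rest on assumed grade distributions, one worst grade per woman, 45 v 60 women, a two-sided 0.05 level and a proportional-odds shift. The direction of the gain was the same for control grade 3 or higher rates of 5.4%, 12% and 26.3%, but it reverses when only the severity of events changes. The primary analysis, its threshold and its stated power are unaffected. This is a specification gap in a supportive comparison, worth closing before analysis.

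**What to change.** In section 4, limit the chi-square clause to binary and unordered outcomes, with Fisher where counts are small, and add wording to this effect:

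- Each woman's worst Clavien Dindo grade, with 0 for no event, is compared between SDD and historical controls by the Wilcoxon/Mann-Whitney test, with an exact or Monte Carlo p-value because of ties.
- The result is reported as a proportional-odds ratio, or the probability that an SDD woman has the worse grade, with a 95% interval.
- Grade 3 or higher v lower is also compared between the groups by chi-square or Fisher.
- A rank comparison among women with an event is reported as supportive, to cover the case where incidence is unchanged but events are worse.

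The last item needs a caution. It conditions on having an event and uses few women: at 35% incidence, about 16 of 45 and 21 of 60. It should describe severity among events and not stand alone.

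The cost is a few sentences. No new data are needed, and the rank test is one the plan already names. The change should be made before the groups are compared.

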## **2. Study Population and Subject Identification**

### **Eligibility Criteria**

Patients of the Center of Urogynecology and Pelvic Reconstructive Surgery in the Department of Ob/Gyn and Women's Health Institute or the Female Urology division in the Department of Urology at the Cleveland Clinic scheduled to undergo a minimally invasive (robotic-assisted or laparoscopic) sacrocolpopexy for pelvic organ prolapse with a board-certified female pelvic medicine and reconstructive surgery specialist will be approached for participation in this study.

Additional surgical procedures may include: hysterectomy (either total or supracervical), trachelectomy, anterior and/or posterior colporrhaphy, enterocele repair, minimally invasive Burch colposuspension or paravaginal defect repair, vaginal mesh removal or revision, vaginal graft placement, midurethral sling, or perineal rectal prolapse repair (Delorme or Altemeier).

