## **6. Research Environment**

SDD and ERAS protocols are part of a new initiative within the Women's Health Institute directed by our chair, [name]. The co-investigator and senior mentor on this project, [name], is the division director and is also committed to the success of this project. Lastly, this project has been discussed at multiple research

meetings and has the support of the other surgeons in the division, some of whom have successfully discharged patients same day after this surgery.

Regarding surgical volume, a chart review determined that ~60 minimally invasive sacrocolpopexies without concomitant rectopexy were performed within our division in 2016. Our Female Urology collaborator, who will be participating in this study, performs ~20 minimally invasive sacrocolpopexies per year. In 2017, we also had two new staff join the urogynecology division, who also perform this surgery and will be participating in subject recruitment. As such, we feel that our target recruitment is an achievable goal. Lastly, there are no current or planned clinical trials that could compete for subject recruitment for this study. Together, we feel that this environment is conducive to the implementation and successful execution of this research study.

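### Aim 2 compares costs with a non-randomised historical cohort, but the plan names no adjustment method that fits a continuous cost and states no common price basis.

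*Combined protocol and SAP*

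**What the plan says.** The Specific Aims section gives Aim 2 a direction: "We hypothesize that the total costs associated with SDD following minimally invasive sacrocolpopexy is less than the same procedure with discharge on POD 1". Costs come from the billing function of the electronic record.

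Section 4 (Statistical Plan) takes the comparator from an earlier randomised mesh trial at the same institution: 60 women, all discharged on postoperative day 1. Of its timing the plan says only "This study completed recruitment 2017".

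For continuous outcomes, section 4 names "an ANOVA analysis or a student's t test for parametric continuous outcomes" and "a Kruskal-Wallis or Mann Whitney U test for non-parametric outcomes". The one sentence on confounding is "Logistic regression will be performed to control for confounding variables". It names neither the outcomes nor the covariates.

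On comparability, section 4 says that the controls match the eligibility criteria, had the same surgical approaches at the same sites, and had operations "performed by the same surgeons as our study". Section 6 (Research Environment) adds: "In 2017, we also had two new staff join the urogynecology division, who also perform this surgery and will be participating in subject recruitment". Eligibility Criteria allows a varied set of added operations: "Additional surgical procedures may include: hysterectomy (either total or supracervical), trachelectomy, anterior and/or posterior colporrhaphy, enterocele repair", and several more.

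The cost outcome is worded in two ways. Specific Aims and section 3 (Data Collection) refer to all costs related to the procedure. The Secondary outcomes list refers to the cost of the operation and the hospital stay after it.

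**The concern.** The two cohorts were not randomised against each other and come from different calendar periods. The plan accepts that confounding needs control, but the method it names models a categorical outcome. Cost could enter a logistic model only if it were dichotomised, which is not planned. ANOVA could be extended with covariates, but it is listed only as a group comparison. Followed as written, the plan therefore yields an unadjusted cost difference.

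Two things could move that difference apart from discharge timing. One is the price level: nothing in the supplied text puts both cohorts on the same basis. The other is the mix of concomitant procedures: the comparability statement covers eligibility, approach, site and surgeon, but not which operations were added. A cost difference could then not be attributed to SDD, and covariates could be chosen after the costs had been seen.

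**Working it through.** **The plan's own figures.** There is no stated figure for Aim 2: no mean cost, SD, target difference or inflation rate. The only sample-size calculation belongs to the primary outcome, and it reproduces. With 45 patients, a 26.3% reference and one-sided 0.05, the exact test rejects at 18 or more events, with power 0.798 at 45.1%; adding 3% dropout gives 47. It says nothing about cost.

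**Inputs from the documents.** 45 SDD patients analysed (47 recruited), 60 controls, two-sided p ≤ 0.05. Control recruitment ended in 2017; its start is not given. SDD recruitment is not dated. The reference list cites a paper that appeared online in February 2018, and the Timeline aims to finish by June 2020, so roughly 2018–2020 is an inference.

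**Assumptions.** Price growth of 2–5% a year over 1–3 years; coefficient of variation (CV) of cost 0.2, 0.3 or 0.5; true saving of 10%, 20% or 30%.

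**Step 1: price drift**, (1 + g)^y − 1.
- 2% for 1 year: 2.0%
- 3% for 2 years: 1.03² − 1 = 6.1%
- 5% for 3 years: 1.05³ − 1 = 15.8%

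**Step 2: apparent difference**, (1 − saving) × (1 + drift) − 1.

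| True saving | Drift 2.0% | Drift 6.1% | Drift 15.8% |
|---|---|---|---|
| 10% | −8.2% | −4.5% | +4.2% |
| 20% | −18.4% | −15.1% | −7.4% |
| 30% | −28.6% | −25.7% | −19.0% |

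**Step 3: chance that Student's t test shows the saving** (simulation, 10,000 runs, lognormal costs, 45 vs 60).

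| True saving, CV | No drift | 2.0% | 6.1% | 15.8% |
|---|---|---|---|---|
| 10%, CV 0.2 | 75% | 57% | 21% | 0.1% |
| 10%, CV 0.3 | 42% | 29% | 12% | 0.4% |
| 10%, CV 0.5 | 19% | 14% | 7% | 0.7% |
| 20%, CV 0.3 | 96% | 93% | 78% | 25% |
| 30%, CV 0.3 | 100% | 100% | 99.9% | 94% |

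**Step 4: precision without any bias.** The 95% half-width is 1.96 × CV × √(1/45 + 1/60) = 0.3865 × CV. That is 7.7%, 11.6% and 19.3% of mean cost at CV 0.2, 0.3 and 0.5.

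**Step 5: case mix.** Bias = difference in prevalence of a concomitant procedure × the share it adds to cost. With 10–30 percentage points and 10–30% of cost, it runs from 0.1 × 0.1 = 1% to 0.3 × 0.3 = 9%, in either direction. With no true difference, a 9% shift in favour of SDD makes the t test show a saving in about 65%, 34% and 16% of studies (CV 0.2, 0.3, 0.5), against a nominal 2.5%. A 3% shift gives 11%, 7% and 5%; a 1% shift gives 3–5%.

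**The case against.** The strongest reply is that much of this rests on silence and on chosen figures. Several stronger readings are tempting, and the documents do not support them.

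- **That the plan commits to a nominal comparison.** It does not. It says only that billing data will be used. What stands is that nothing in the supplied text rules out using amounts as recorded.
- **That price drift could produce a false saving.** If prices rose, the later SDD cohort looks dearer, so drift works against the hypothesis.
- **That drift would defeat Aim 2.** The near-zero power in Step 3 needs both a saving of only 10% and the extreme drift. At a 10% saving and CV 0.3, power is 42% even without drift, so sample size already accounts for most of the failure to detect.
- **That the surgeons differ.** Section 4 says they are the same. The two staff who joined in 2017 may have operated on controls; the text does not say. A different surgeon mix is a possibility only.
- **That the cost outcome is undefined, or that the wordings conflict outright.** The Secondary outcomes wording may be shorthand, and the data collection sheet, which section 3 cites and which was not supplied, may list components. Emergency and unscheduled visits are separate outcomes, so such use stays visible even if it is not costed.
- **That the rank-test option would manufacture savings.** That needs many costly post-discharge events on the SDD side alone, which nothing in the documents suggests. The retrospective study in the Background found no difference in visits or readmissions. What remains is that a rank test does not estimate a difference in mean cost.

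It is also fair that the case-mix gap in Step 5 has no figure behind it in the documents. The mechanism stands, because concomitant procedures vary and the comparability statement does not cover them. The size is unknown.

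**Conclusion.** The point holds for Aim 2. Section 4 specifies no analysis that adjusts a continuous cost for confounding, and the supplied text gives no common price basis for cohorts from different periods.

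The price effect, if billed amounts are used as recorded and prices rose, runs against SDD and can mask a saving. It is small for a 20–30% saving with mild drift, and large only for a small saving or strong drift. The case-mix effect can run either way and is the part that could create an apparent saving: 1% to 9% of mean cost under the stated assumptions, negligible at the lower end. The difference in cost wording is a lesser matter of consistency.

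Every size rests on assumed drift, cost variation, saving and case mix. Cost is a secondary outcome, and the primary safety conclusion is unaffected. The change is worth making because it is cheap and because without it a cost difference cannot be attributed to discharge timing.

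**What to change.** In section 4:

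1. State that both cohorts' costs will be expressed in one named price year, or built from one unit-cost schedule.
2. Make the main Aim 2 analysis the adjusted difference in mean cost (SDD minus day-1 discharge) with a 95% CI. Use either linear regression with a bootstrap CI, or a gamma model with log link followed by standardised (marginal) means. The standardisation is needed because the log-link model by itself gives a ratio.
3. List a few concomitant-procedure covariates, such as hysterectomy and midurethral sling, fixed before costs are extracted.
4. Keep the t test or rank test as a sensitivity analysis, and reserve logistic regression for binary outcomes.

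In Specific Aims, Secondary outcomes and section 3, use one cost definition (components and time window), applied identically to both cohorts.

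**Cost.** Wording changes, a price conversion and one regression model, with a billing query for 47 + 60 = 107 patients that may need widening to fit the definition. No added patients or visits.

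**Downside.** About 45 + 60 = 105 analysed patients support only a few covariates, so some confounding will remain. The estimated saving may move in either direction. Adjustment also does not settle how patients kept overnight, or excluded for intraoperative events, count in the SDD cost group; the definition should say.
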